**Table 3: Laboratory Parameters: Criteria for Markedly Abnormal Values**

Laboratory Parameter	Markedly Low	Markedly High
Albumin (g/L)	<20	> 2 x ULN
Alkaline phosphatase (U/L)	N/A	> 1.5 x ULN
Alanine aminotransferase (ALT) (U/L)	N/A	> 3 x ULN
Aspartate aminotransferase (AST) (U/L)	N/A	> 3 x ULN
Bicarbonate [mmol/L]	15.1	34.9
Bilirubin (umol/L)	N/A	> 1.5 x ULN
Urea Nitrogen (mmol/L)	N/A	> 3 x ULN
Calcium (mmol/L)	<1.75	>3
Chloride (mmol/L)	<90	>120
Creatine kinase (U/L)	N/A	> 3 x ULN
Creatinine (umol/L)	N/A	> 1.5 x ULN
Gamma glutamyl transferase (U/L)	N/A	> 3 x ULN
Glucose (mmol/L)	<3.33	> 3 x ULN
Lactate dehydrogenase (U/L)	N/A	> 1.5 x ULN
Phosphate (mmol/L)	<0.484	> 1.5 x ULN
Potassium (mmol/L)	<2.8	>5.8
Protein (g/L)	N/A	> 2 x ULN
Prothrombin International Normalized Ratio	N/A	≥1.3
Sodium (mmol/L)	<125.0	>155.0
Hemoglobin (g/L)	<75	> 1.1 x ULN
Platelets (x10e9/L)	<100	> 3 x ULN
Erythrocytes (x10e12/L)	<3	> 2 x ULN
Leukocytes (x10e9/L)	<2.5	> 2.5 x ULN
Hematocrit [fraction]		
male	0.24	0.55
female	0.28	0.5

Graphical presentations will be created for the following liver function tests: alanine aminotransferase, aspartate aminotransferase, albumin, bilirubin, alkaline phosphatase, gamma glutamyl transferase. Liver function test results standardized to the upper limit of normal (based on central laboratory ranges) will be graphically presented over time for each subject. The incidence of liver function tests above the central laboratory normal limit will be presented by treatment group at each scheduled time point and endpoint.

Graphical presentations will also be created for prothrombin international normalized ratio results.

Clinical laboratory tests that meet the criteria for abnormal and markedly abnormal will be listed by subject. Results on urine drug screen, alcohol screen and pregnancy test will be presented in separate listings.

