JNJ-42165279 C_{max} was reached at 0.5 to 2.5 hours postdose (median t_{max} value, 0.75 hours) following single-dose and once-daily administration of 100 mg. Based on the trough (i.e., predose) concentrations, steady-state conditions were achieved by the third 100-mg daily dose of JNJ-42165279. On average, the C_{max} and AUC_{τ} values were 1.13-times and 1.44-times higher on Day 6 relative to Day 1. The similarity between the mean AUC_{∞} following the 100-mg dose during Part 1 (8,419 ng.h/mL) and the mean AUC_{τ} on Day 6 during Part 2 (8,644 ng.h/mL) further suggests that the pharmacokinetics of JNJ-42165279 is consistent after single-dose and once-daily repeated administration.

At a dose level of 30 mg or higher, FAAH activity in white blood cells (WBCs) showed a significant decrease with duration of at least 24 hours. At the same time the FAA plasma levels showed a significant increase.

JNJ-42165279 was found to be well tolerated. There were no clinically significant changes in any safety measurements, including clinical laboratories, electrocardiograms (ECGs), vital signs, and physical and neurological examinations. There were no changes or abnormal findings in blood coagulation parameters. There were no deaths, serious adverse events (SAEs), or discontinuations due to adverse events. All adverse events reported were mild in severity and had resolved by the time of the follow-up visit. The most frequently reported adverse events for subjects receiving JNJ-42165279 were headache, nasal congestion, and dizziness.

In the second multiple ascending dose (MAD) study 42165279EDI1002, five cohorts were studied: healthy males at 10 mg, 25 mg, and 75 mg; healthy females (non-child bearing potential) at 100 mg, and healthy elders at 100 mg. Six subjects were on active and two on placebo in each cohort. All subjects were dosed during 10 days and cerebrospinal fluid (CSF) sampling was conducted prior to dosing and after 7 days of dosing in the healthy male cohorts. Concentrations of JNJ-42165279 in plasma, urine, and CSF were measured; and FAAH activity in leucocytes (WBCs), and anandamide (AEA), N-oleoylethanolamide (OEA), N-palmitoylethanolamide (PEA) in plasma, and AEA, OEA, and arachidonic acid (AA) in CSF were assayed. Tolerability, including effects on cognition and subjective ratings, were assessed. As dose related increases in coagulation parameters had been observed in male rats, blood coagulation parameters were also included.

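### SAP 5.3: the liver-test incidence table counts albumin only when it is high, and the low hematocrit limits in Table 3 run against the table's own ordering of the sexes

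*SAP*

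**What the plan says.** SAP 5.3 flags treatment-emergent markedly abnormal (TEMA) values with sponsor-defined limits listed in Table 3, whose columns are "Laboratory Parameter Markedly Low Markedly High". A value is TEMA mainly when the baseline is missing or normal and a later value crosses the limit.

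- **Hematocrit** is split by sex: "male 0.24 0.55" and "female 0.28 0.5".
- **Albumin** has limits in both directions: "Albumin (g/L) <20 > 2 x ULN". The other five liver tests have a high limit only, for example "Alanine aminotransferase (ALT) (U/L) N/A > 3 x ULN".

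Below Table 3, the SAP names six liver function tests: ALT, AST, albumin, bilirubin, alkaline phosphatase (ALP) and gamma glutamyl transferase (GGT). It plots each subject's results over time relative to the upper limit of normal (ULN), and then states: "The incidence of liver function tests above the central laboratory normal limit will be presented by treatment group". That paragraph plans no count of values below normal.

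Low values are covered elsewhere. SAP 5.3 has shift tables with below, within and above classes, and listings of abnormal values. Protocol 11.3 promises, for each analyte and by treatment group, the number and percentage of subjects below or above the reference range.

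**The concern.** **Albumin.** Of the six tests, albumin is the one for which a fall is the finding to look for in a liver display. Table 3 supports this, since albumin alone has a low limit. Programmed as written, the liver incidence table adds a subject when albumin rises above normal and adds nothing when it falls below. Someone who reads only that table would see an albumin row that cannot show the relevant change.

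**Hematocrit.** By splitting the row by sex and placing the high limit higher for men, the table implies that men's values run higher. The low limits then go the other way, so the same low value can be flagged in a woman and pass in a man. Both sexes are enrolled, and randomization is stratified by (pooled) center and lead-in response status, not by sex. A difference in sex mix between arms could therefore move the count slightly.

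At stake is whether two prespecified safety displays show what a reader would take them to show.

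**Working it through.** The plan states no figure to reproduce here. The check reads Table 3 against the text below it, with hand arithmetic on the four hematocrit limits.

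**Albumin: where each result is counted, from a normal baseline**

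| Post-baseline albumin | Liver incidence table | Table 3 (TEMA) | Shift tables and protocol 11.3 summary |
|---|---|---|---|
| Above ULN, up to 2 x ULN | 1 | not flagged | above |
| From 20 g/L up to the lower limit of normal | 0 | not flagged | below |
| Under 20 g/L | 0 | markedly low | below |

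The middle row matters most: such a fall is missed by both the liver table and TEMA, and shows only in the general displays.

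**Hematocrit: order of the sexes**

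- High limits: 0.55 − 0.50 = +0.05, so the limit for men is higher.
- Low limits: 0.24 − 0.28 = −0.04, so the limit for men is lower.
- At 0.26: 0.26 < 0.28, so a woman is flagged; 0.26 > 0.24, so a man is not. The value lies strictly between the two limits, so the result does not depend on whether a limit itself counts as abnormal.

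**Is a transposition plausible?**

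| | Men: width (high − low) | Men: low/high | Women: width (high − low) | Women: low/high |
|---|---|---|---|---|
| As printed | 0.55 − 0.24 = 0.31 | 0.24/0.55 = 0.44 | 0.50 − 0.28 = 0.22 | 0.28/0.50 = 0.56 |
| Low values exchanged (illustration only) | 0.55 − 0.28 = 0.27 | 0.28/0.55 = 0.51 | 0.50 − 0.24 = 0.26 | 0.24/0.50 = 0.48 |

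Exchanging the low values makes the two bands nearly equal and puts both limits in the same sex order. This is a heuristic. Nothing in the documents requires widths or ratios to match between the sexes.

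**Do other red-cell flags close the gap?** Table 3 has low limits without a sex split for erythrocytes (<3 x10e12/L) and hemoglobin ("Hemoglobin (g/L) <75 > 1.1 x ULN"). Hematocrit equals erythrocyte count times mean corpuscular volume (MCV). At the erythrocyte limit of 3, an assumed MCV of 80, 90 or 100 fL gives a hematocrit of 0.24, 0.27 or 0.30. For a man at 0.26, the count is 0.26/0.080 = 3.25 at 80 fL (not flagged) and 0.26/0.090 = 2.89 at 90 fL (flagged). The overlap is therefore partial and depends on MCV, which the documents do not give.

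**The case against.** The case against has several sound parts.

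- **Low albumin is not lost.** A reader might infer that the safety analysis cannot see it. The documents do not support that: the shift tables, the <20 g/L flag, the listings and the protocol 11.3 summary all cover it. What is left is the content of one table.
- **The plots do not hide a fall.** Dividing by the ULN rescales the values, so falling albumin still appears as a falling line. Only the incidence count has the wrong direction.
- **The hematocrit limits are sponsor-defined, and the source standard is not among the documents.** It is tempting to conclude that the two low values were swapped and should be swapped back. The documents cannot show this. The standard may contain 0.24 and 0.28, or a single digit may be wrong, and in either case an exchange would introduce a new error.
- **The safety rationale should not be stretched.** A reader might link hematocrit to the rat coagulation findings. The protocol sentence "As dose related increases in coagulation parameters had been observed in male rats, blood coagulation parameters were also included" describes a Phase 1 study and is not about hematocrit. Protocol 1.1 reports no coagulation changes in either Phase 1 dose-escalation study, and INR has its own flag and plots in SAP 5.3. Likewise, the liver signal in protocol 16.1 (5 of 30 exposed, 1 of 10 on placebo) is transaminase elevation, which the liver table counts in the right direction. The individual liver stopping criteria in protocol 3.3.1 use AST, ALT and bilirubin, so albumin plays no part in them.

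These arguments limit the point without removing it. The liver table as written still counts albumin only when high, and Table 3 still reverses its own ordering of the sexes without explanation.

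**Conclusion.** Both defects stand, and both are minor. The albumin defect is confined to the liver-specific incidence table. The hematocrit defect is an unexplained inconsistency: the flag does detect low values in both sexes, but between 0.24 and 0.28 it treats men and women differently, against the order set by the high limits. A transposition is plausible and unproven.

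The documents give no expected number of affected subjects. The hematocrit issue needs a man with a normal baseline who falls into that narrow range, so the judgement here is none to a handful. At that number, a chance imbalance of the sexes between arms would hardly matter. The primary efficacy analysis and the stopping criteria are unaffected.

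The conclusion rests on two readings: that low albumin is the informative direction, which agrees with albumin being the only liver test given a low limit; and that the sexes should be ordered alike at both ends of the hematocrit row, which is inferred from the high limits.

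**What to change.** Make two text edits in SAP 5.3 before unblinding.

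1. **Liver incidence table:** present the incidence of albumin below its lower limit of normal, and keep above normal for ALT, AST, bilirubin, ALP and GGT. Optionally, also plot albumin against its lower limit.
2. **Table 3, hematocrit:** reconcile the row with the sponsor's source criteria. If it was mis-transcribed, correct it to the source. If the source has the same values, state this in the SAP and show hematocrit TEMA by sex, so that the different limits are visible to the reader.

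The cost is a check against one source document, two wording changes and a small programming update. No new data are needed.

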#### **Rule for BQL/UQL (if applicable)**

For the measurement that is BQL/UQL, the value will be imputed based on the lowest/highest limit of quantifiable value for the summary table, e.g. if the original result of measurement is marked as '<0.1', the value will be imputed as 0.1 correspondingly. For the listing, however, the original values as stated in the database will be presented.

#### **5.4. Vital Signs and Physical Examination Findings**

Descriptive statistics for absolute values and changes from baseline will be presented at each scheduled time point and endpoint by treatment group and study period for body weight, supine systolic blood pressure (mmHg), supine diastolic blood pressure (mmHg), pulse rate (beats per minute) and oral temperature (°C).

Mean-SE plots over time will be presented for vital sign values by treatment group. In addition, scatter plots of post-baseline versus baseline values will be presented by treatment group. All individual vital signs data will be listed.

Abnormal values are defined in Table 4 and will be summarized using frequency distribution tables over time by treatment group and study period. A listing of subjects meeting any of the abnormality criteria will be provided.

**Table 4: Vital Signs Abnormality Ranges (Supine and Standing)**

	Low	Normal	High
SBP (mmHg)	<90	90-140	>140
DBP (mmHg)	<50	50-90	>90
Pulse (bpm)	<45	45-90	>90
Temperature (C)	<35.5	35.5-37.5	>37.5

The incidence of subjects who have a treatment-emergent abnormality (as defined in Table 5 below) at each scheduled time point and endpoint will be presented by treatment group and study period.

**Table 5: Treatment-Emergent Abnormality Categories for Vital Signs**

Vital Parameter	Post-baseline value outside of normal limit if:	
	Abnormally low	Abnormally high
Pulse (bpm)	A decrease from baseline of $\geq 15$ to a value $< 45$	An increase from baseline of $\geq 15$ to a value $> 90$
Systolic BP (mmHg)	A decrease from baseline of $\geq 20$ to a value $< 90$	An increase from baseline of $\geq 20$ to a value $> 140$
Diastolic BP (mmHg)	A decrease from baseline of $\geq 15$ to a value $< 50$	An increase from baseline of $\geq 15$ to a value $> 90$

Physical and neurological examination abnormalities will be listed. If a subject has an abnormality noted at any time, all the observations will be listed.

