9.2.5. Physical and Neurological Examinations^a

The study investigator or other authorized and appropriately qualified designee will perform the physical examination.

Height will be measured at screening only. Body weight will be measured as per the Time and Events schedule.

The neurological examination can be adapted as necessary but should include mental status (orientation and memory); oculomotor motion and vision for cranial nerve testing; limb strength and abnormal movements for motor function; and tests of cerebellar function: gait, finger-to-nose, heel-to-shin, and rapid alternating movements. Tests of sensation (e.g., pain, vibration) should be included only if indicated by clinical history/symptoms.

The neurological examination will be done at screening, during the treatment phase and at the end of treatment visit (or early withdrawal visit) for all subjects. In addition, neurological examinations will be completed when event driven. These events of interest include diplopia, vision impairment, gait disturbance and severe headache.

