Summaries will be provided for all subjects receiving at least one dose of study drug in this study.

Data listings of subjects with any potentially clinically important values (QTc value >450, >480, or >500 msec) or with a change from baseline in QTc >30 msec will be provided.

Vital Signs

Descriptive statistics of pulse, supine blood pressure (systolic and diastolic), temperature and body weight values and changes from baseline will be summarized at each scheduled time point.

Physical and Neurological Examinations

The number and percentage of subjects with a change from normal at baseline to abnormal at any post-baseline exam will be tabulated by treatment group.

Subjects with abnormal findings will be presented in a data listing.

Columbia Suicide Severity Rating Scale (C-SSRS)

Results from the C-SSRS will be tabulated by treatment group for all subjects receiving at least one dose of study drug in this study.

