12.2. Special Reporting Situations^a

Safety events of interest on a sponsor study drug that may require expedited reporting and/or safety evaluation include, but are not limited to:

Overdose of a sponsor study drug

Suspected abuse/misuse of a sponsor study drug

Inadvertent or accidental exposure to a sponsor study drug

^a This section has been amended per Amendment INT-2.

Medication error involving a sponsor product (with or without subject/patient exposure to the sponsor study drug, e.g., name confusion)

For this study safety events of interest include diplopia, vision impairment, gait disturbance and severe headache. These events will trigger a neurological examination and a narrative of the event.

Special reporting situations should be recorded in the CRF. Any special reporting situation that meets the criteria of a serious adverse event should be recorded on the serious adverse event page of the CRF.

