- The following TEAEs are considered to be of special interest in this study: severe headache, change in mental states, change in sensory function, change in motor function or coordination. The number (%) of subjects with TEAEs of special interest will be summarized by system organ class and preferred term for each treatment group and study period. Listings will be created with the results of neurological examinations following the incidence of these AEs.
- Data listings will be generated for all AEs, deaths, serious adverse events (SAEs), severe AEs and discontinuations due to AEs and AEs of special interest. These listings will not be limited to TEAEs but will also include any adverse events with onset before the start of study treatment or after the end of study treatment. If there is no data to present then the listing should be created and should state "No data to present".

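### SAP 5.4 replaces the by-arm exam table promised in Protocol 11.3 with a listing, and SAP 5.2 names different neurological events of interest from the protocol without mapping terms

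*SAP*

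**What the plan says.** **Exam results.** Protocol 11.3, under Physical and Neurological Examinations, commits to the number and percentage of subjects with a "change from normal at baseline to abnormal at any post-baseline exam will be tabulated by treatment group". It then adds a second output: "Subjects with abnormal findings will be presented in a data listing". SAP 5.4, in the text below Table 5, has one output: "Physical and neurological examination abnormalities will be listed". It adds that once a subject has any abnormality, all of that subject's observations are shown. SAP Table 1 assigns analysis windows to the neurological exam at screening, double-blind Week 2, double-blind Week 6 and withdrawal Week 2.

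**Events of interest.** Protocol 12.2 states: "For this study safety events of interest include diplopia, vision impairment, gait disturbance and severe headache". These events trigger a neurological exam and a narrative. Protocol 9.2.5 names the same four. SAP 5.2 instead takes as TEAEs of special interest "severe headache, change in mental states, change in sensory function, change in motor function or coordination". It plans that "TEAEs of special interest will be summarized by system organ class and preferred term for each treatment group and study period", and it lists the results of neurological exams that follow such events.

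**The concern.** Safety and tolerability are part of the primary objective (Protocol 2.1, SAP 1.1). SAP 1.4 records that the study was suspended after severe safety issues with another FAAH inhibitor. Amendment INT-2 then added neurological exams to confirm that participation and treatment were safe. A safety reader will look for the results of those exams by arm, and the SAP plans no table of them.

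A listing is a poor substitute. It holds only subjects with at least one abnormality, it shows findings present at screening next to new ones, and it does not say how many subjects per arm were examined and normal at the start.

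The event lists raise a smaller problem of the same kind. Without a mapping, someone must decide later which preferred terms belong to which SAP category. Diplopia, for example, could be placed under sensory function or under motor function. If that is decided after unblinding, the counts in the special-interest table are open to choice.

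**Working it through.** The plan gives no figure to reproduce here. The check sets the two documents side by side.

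**Step 1. Planned outputs for exam results.**

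| Output | Protocol 11.3 | SAP 5.4 |
|---|---|---|
| n (%) normal to abnormal, by arm | 1 table | none |
| Listing of abnormal findings | 1 listing | 1 listing |

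**Step 2. Is the table elsewhere in the SAP?** No. SAP 5.2 only lists exams that follow a special-interest event. No SAP table uses the neurological windows in Table 1. Laboratory tests (SAP 5.3), vital signs (5.4), ECG (5.5) and C-SSRS (5.6) all have summaries by treatment group; physical and neurological exams do not.

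**Step 3. Can the comparison be rebuilt from the listing?** The numerators can be counted by hand. The denominator cannot: subjects who were normal throughout do not appear. SAP 3.2 gives analysis-set and disposition counts, but not the number with a normal screening exam and at least one later exam.

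**Step 4. Which baseline, and which exams?** From the Time and Events Schedule and SAP Table 1:

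| Exam | Before double-blind dosing | Afterwards |
|---|---|---|
| Neurological | Screening | Visits 7 and 9 (double-blind), Visit 10 or early withdrawal, plus event-driven |
| Physical | Screening | Visit 10 or early withdrawal, and Visit 11 (follow-up) |

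Neither exam is scheduled on Day 1 or at double-blind baseline (Visit 5). SAP 2.4 takes the closest measurement before the first dose of each period, so for scheduled exams the double-blind baseline falls back to screening. An event-driven exam during lead-in could displace it, so the table should name screening explicitly. Two consequences follow. First, an abnormality at Visit 7 may have begun during the placebo lead-in, which SAP 1.2 gives as 3 weeks. Randomization balances this between arms on average, so the comparison remains valid. Second, a subject who completes the double-blind period has the Visit 10 exam after the placebo withdrawal period, so it answers a different question from Visits 7 and 9.

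**Step 5. Event lists.**

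| Protocol 9.2.5 and 12.2 | SAP 5.2 |
|---|---|
| Severe headache | Severe headache |
| Diplopia | Sensory or motor function (assumed) |
| Vision impairment | Sensory function (assumed) |
| Gait disturbance | Motor function or coordination (assumed) |
| Not named | Mental states |

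One of four protocol terms is named in both lists. The other placements are assumptions, because the SAP gives no mapping.

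**The case against.** The strongest reply is that the arms are still compared through adverse events. Protocol 9.2 requires clinically relevant changes to be recorded as adverse events. SAP 5.2 tabulates all TEAEs, and separately those of special interest, by system organ class, preferred term, treatment group and study period. This stands. A reader might infer that the added neurological monitoring yields no comparison at all, or that diplopia, vision impairment and gait disturbance would go uncounted. The documents support neither: each would appear in the general TEAE table under its preferred term, whatever grouping is used.

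It can also be said that the protocol's lists are open, since both use the word include, and that Protocol 9.1.1 allows extra measurements after abnormal safety findings. So it would go too far to say that a mental-state change cannot lead to an exam; it is only not a named trigger. The SAP categories also resemble the exam domains in Protocol 9.2.5 and may be meant as a broader set. This stands too, and it reduces the second part of the point to a missing mapping.

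Finally, Protocol Section 11 leaves specific details to the SAP, and nothing in Amendment INT-2 says that a randomized comparison of exam changes was the purpose of the exams. The second part is fair. The first does not help, because dropping a stated output is not a matter of detail. Nor does the adverse-event route replace the table. It passes each finding through the investigator's judgment of relevance and through coding, and it does not give the proportion of subjects who moved from normal to abnormal.

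**Conclusion.** The point holds in a limited form. One by-arm output promised in Protocol 11.3, covering two types of exam, is absent from the SAP, and the available text gives no reason. The special-interest list matches the protocol's on one named term of four, with no mapping. What is lost is the between-arm comparison and denominator for the exam results. Adverse events remain compared by arm, and the efficacy analysis is untouched.

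A reader might also picture a listing of every randomized subject. SAP 5.4 does not say that: it covers only subjects with an abnormality, which is why it has no denominator.

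The conclusion rests on the text as supplied. Some SAP pages were not available, so an explanation there cannot be excluded. No estimate is made of how many new abnormalities would occur, since the documents give no rate.

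**What to change.** 1. In SAP 5.4, restore the Protocol 11.3 table for physical and neurological exams as n/N (%) by treatment group, and keep the listing. Name screening as baseline, and define N; for example, randomized subjects with a normal screening exam and at least one exam in the period shown.
2. For neurological exams, count any post-baseline exam, as the protocol states. Also show the double-blind exams (Visits 7 and 9, plus early-withdrawal and event-driven exams) apart from withdrawal Week 2.
3. For physical exams, use those actually scheduled: Visit 10 or early withdrawal, and follow-up.
4. In SAP 5.2, add the four protocol-named events as rows in the by-arm special-interest table alongside the SAP categories, and fix the preferred terms for each row before unblinding.
5. Reconcile SAP 5.2 with Protocol 9.2.5 and 12.2 on which events are of interest. Which events should trigger an exam is for the sponsor to settle; no view is taken here.
6. If the table was dropped on purpose, say so in the SAP and give the reason.

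The cost is one or two descriptive tables and a short term list, all from data already collected.
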